5.2.6.4 Laboratory safety variables

Table of laboratory safety variables:

Laboratory evaluations will be summarized by visit and by treatment group on the SAF population. For each hematology, chemistry and coagulation variables we will compute:

- Quantitative descriptive statistics on both raw values and change from baseline (Statistical tables 14.3.8.1-2, 14.3.9.1-2 and 14.3.10.1-2)
- Qualitative descriptive statistics (individual patient changes):
 - Number of patients with values: normal, abnormal NCS, abnormal CS (Statistical table 14.3.8.2, 14.3.9.2 and 14.3.10.3)
 - Shift Tables from baseline to each visit (Statistical table 14.3.8.3, 14.3.9.3 and 14.3.10.3)

Depending of their number the clinically significant laboratory abnormalities will not be tabulated but rather presented in individual data listings (Listings 16.2.8.1 to 16.2.8.4).

Figures on laboratory safety variables:

All individual values of a given laboratory measurement for each patient will be produced. When available, the LLN and ULN will be displayed on the graph. Figures will be produced for all hematologic, chemistry and coagulation variables (Figures 14.3.2).

To facilitate the exploration of potential Drug-Induced Liver Injury (DILI), eDISH (Evaluation of Drug-Induced Serious Hepatotoxicity) plots, plotting peak total bilirubin level versus peak ALT level, both expressed as multiples of the upper limit of normal on a base 10 logarithmic scale, together with mlines identifying the normal range and 2 times the upper lipit of the normal range for total bilirubin and three times the upper limit of the normal range for ALT, will be presented (Figure 14.3.3).

Listing of laboratory safety variables:

Listings of all safety-related laboratory test including pregnancy test (Listings 16.2.8.1 to 16.2.8.4) will be prepared, presenting patient id, identification of time point, age, sex, race-ethnicity, weight, identification of laboratory test, raw result, evaluation (normal, abnormal...), investigator judgment on clinical significance on abnormal values. This listing will be presented by treatment group.

5.2.6.5 Physical exams

For all the variables collected during physical examinations at baseline, the frequencies of normal, abnormal NCS and abnormal CS values will be reported by treatment group (Statistical table

14.3.11). All individual measurements collected at baseline and during the subsequent visits will be provided in Listing 16.2.9.1.

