7.7. Physical Examination

A complete physical examination is to be performed during Screening and an abbreviated physical exam thereafter. The complete physical examination is to include measurement

of height during Screening. Weight is to be measured throughout the study for use in weight based dose calculations.

Complete physical examinations also will include a review of the following body systems:

- General appearance.
- Head, eyes, ears, nose, and throat.
- Respiratory.
- Cardiovascular.
- Abdomen.
- Neurologic.
- Extremities.
- Dermatologic.

Full physical examinations are to be performed at screening; Abbreviated physical exams are to be performed thereafter.

The findings of each examination are to be documented in the eCRF.

If an abnormality noted on physical examination is considered by the Investigator to be clinically significant, then the abnormality is to be recorded as part of the subject's medical history if occurring prior to start of dosing and as an AE occurring if after the start of study drug administration at Week 0, where the finding represents a change from Baseline. Any worsening of a baseline medical condition during the study should be recorded as an adverse event.

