5.2 Planned analysis

5.2.1 Demographics and baseline characteristics

The following demographics variables will be summarised by treatment group on the ATS, SAF and the PP analysis data sets (Statistical tables 14.1.1 to 14.1.3):

- Gender
- Age
- Ethnicity / Race
- Number of years since diagnosis of IPF

The following baseline characteristics will be summarised by treatment group on the ATS analysis data set:

- Vital signs (including Weight and Height) at baseline by treatment group (Statistical table 14.1.2)
- Physical exam at baseline by treatment group (Statistical table 14.1.3)
- Haematology at baseline by treatment group (Statistical table 14.1.4)
- Haematology abnormalities at baseline by treatment group (Statistical table 14.1.5)
- Chemistry at baseline by treatment group (Statistical table 14.1.6)
- Chemistry abnormalities at baseline by treatment group (Statistical table 14.1.7)
- Coagulation at baseline by treatment group (Statistical table 14.1.8)
- Coagulation abnormalities at baseline by treatment group (Statistical table 14.1.9)
- Background therapy - Use of nintedanib and pirfenidone prior to baseline (Statistical table 14.1.10)

The following baseline characteristics will be summarised by treatment group on the ATS and the PP analysis data sets:

- King's Brief interstitial Lung Disease (Statistical table 14.1.11.1.1 to 14.1.11.1.2) and Leicester Cough Questionnaire (Statistical table 14.1.11.2.1 to 14.1.11.2.2) results at baseline by treatment group.
- High Resolution Computed Tomography measurements at baseline by treatment group (Statistical table 14.1.12.1 to 14.1.12.2)
- Pulmonary Function Tests at baseline by treatment group (Statistical table 14.1.13.1 to 14.1.13.2)
- Six-minute Walk Test distance at baseline by treatment group (Statistical table 14.1.1 to 14.1.2)
- Pentraxin-2 levels at baseline by treatment group (Statistical table 14.1.15.1 to 14.1.15.2)

The following baseline characteristics will be summarised by treatment group on the SAF, the ATS and the PP analysis set:

- Anti-Pentraxin 2 antibodies (ADA) at baseline by treatment group (Statistical table 14.1.16.1 to 14.1.16.3)
- Baseline Genetic Status by treatment group (Statistical table 14.1.17.1 to 14.1.17.3)
- Biomarker levels at baseline by treatment group (Statistical table 14.1.18.1 to 14.1.18.3)

All demographics variables and genetic characteristics of each patient (when available for analysis) will be reported in listing 16.2.4.1 and 16.2.4.2 respectively.

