5.2.6 Safety analyses

Safety analysis will be based on the incidence, intensity, and type of adverse events, incidence of respiratory decline, Infusion related reactions, and clinically significant changes in the subject's physical examination, vital signs and clinical laboratory results. Safety variables will be tabulated and presented for all subjects who have received any amount of study medication.

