5.2.6.1 Adverse events

Adverse event listings:

AE listings will be presented and sorted by treatment group, subject, primary system organ class, preferred term and verbatim text for all adverse events recorded during the study and will include duration of each episode.

The following listings will be produced:

- Listing of Adverse Events (Listing 16.2.7.1): All adverse events for each patient, including the same event on several occasions, giving both preferred term and the original term used by the investigator. The listing will be sorted by site and by treatment group and should include: Patient identifier / Age, race-ethnicity, sex, weight, height / The adverse event (preferred term, reported term) / Duration of the adverse event / Severity (mild, moderate, severe) / Seriousness (serious, non-serious) / Action taken with study drug (dose reduced, treatment interrupted-delayed, treatment permanently discontinued-omitted, none, not applicable) / Outcome (resolved, resolved with sequelae, ongoing, unknown) / Relationship to study drug (not related, possibly related, probably related) / Date of onset or date of clinic visit at which the event was discovered / Timing of onset of the adverse event.
- Listing of Deaths (Listing 16.2.7.2) and Serious Adverse Events containing the same information as above.

Adverse events tabulations:

Tabulation of adverse events will present for each cell the following information: number of patients with at least one occurrence of the event, corresponding percentage and number of events (if relevant). The following tables will be produced for the whole SAF population as well as by treatment group:

Summary of AE (Statistical Table 14.3.3):

- Any AE
- Any TEAE
- Any TEAE leading to permanent study treatment discontinuation
- Any TEAE leading to study discontinuation
- Any TEAE of severe intensity
- Any possibly or probably related TEAE
- Any SAE
- Any TESAE
- Any TESAE leading to study treatment permanent discontinuation
- Any TESAE leading to study discontinuation (optional)
- Any TESAE considered related to the study treatment
- Deaths (if any)
-

Detailed Tables on TEAEs:

- All TEAE by SOC and PT (Statistical Table 14.3.4.1)
- Most frequent TEAEs by SOC and PT and decreasing frequency (Statistical Table 14.3.4.2)
- All possibly or probably related TEAEs by SOC and PT (Statistical Table 14.3.4.3)
- All TEAE by SOC, PT and intensity (Statistical Table 14.3.4.4)

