14.2.29.1.3.1.d to 14.2.29.1.3.2.d	(EOA) Additional Exploratory Efficacy Analysis: Forced Vital Capacity (% predicted FVC) - Separately for each stratum - Least Square Means for change from baseline at each visit - Nintedanib
14.2.29.2.1.1 to 14.2.29.2.1.2	(EOA) Additional Exploratory Efficacy Analysis: Forced Vital Capacity (% predicted FVC) - raw value at each visit - Pirfenidone

14.2.29.2.2.1 to 14.2.29.2.2.2	(EOA) Additional Exploratory Efficacy Analysis: Forced Vital Capacity (% predicted FVC) - change from baseline - Pirfenidone
14.2.29.2.3.1.a to 14.2.29.2.3.2.a	(EOA) Additional Exploratory Efficacy Analysis: Forced Vital Capacity (% predicted FVC) - Separately for each stratum - Anova table - Pirfenidone
14.2.29.2.3.1.b to 14.2.29.2.3.2.b	(EOA) Additional Exploratory Efficacy Analysis: Forced Vital Capacity (% predicted FVC) - Separately for each stratum - Model parameter estimates - Pirfenidone
14.2.29.2.3.1.c to 14.2.29.2.3.2.c	(EOA) Additional Exploratory Efficacy Analysis: Forced Vital Capacity (% predicted FVC) - Separately for each stratum - Least Square Means at each visit - Pirfenidone
14.2.29.2.3.1.d to 14.2.29.2.3.2.d	(EOA) Additional Exploratory Efficacy Analysis: Forced Vital Capacity (% predicted FVC) - Separately for each stratum - Least Square Means for change from baseline at each visit - Pirfenidone
14.2.30.1.1 to 14.2.30.1.2	(EOA) Additional Exploratory Efficacy Analysis: Historic Forced Vital Capacity (% predicted FVC) – Model parameter estimates
14.2.30.2.1 to 14.2.30.2.2	(EOA) Additional Exploratory Efficacy Analysis: Historic Forced Vital Capacity (ml) – Model parameter estimates
n°	SAFETY RESULTS
14.3.1	Extent of exposure
14.3.2.1 to 14.3.2.3	Pentraxin-2 levels over time
14.3.3	Summary of Adverse Events
14.3.4.1	Treatment Emergent Adverse Events (TEAEs) by System Organ Class (SOC) and Preferred Term (PT)
14.3.4.2	Frequent Treatment Emergent Adverse Events (TEAEs) (>5% Overall) by System Organ Class (SOC) and Preferred Term (PT)
14.3.4.3	Possibly or Probably Related Treatment Emergent Adverse Events (TEAEs) by System Organ Class (SOC) and Preferred Term (PT)
14.3.4.4	Treatment Emergent Adverse Events (TEAEs) by System Organ Class (SOC), Preferred Term (PT) and Intensity
14.3.4.5	Treatment Emergent Adverse Events (TEAEs) Leading to Permanent Study Drug Discontinuation by System Organ Class (SOC) and Preferred Term (PT)
14.3.4.6	All TEAEs leading to permanent study discontinuation by SOC and PT

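### The only safety table for physical examination (Table 14.3.11) is restricted to baseline, so no planned table compares the arms on post-baseline examination findings

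*SAP*

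**What the plan says.** **Physical examination.** SAP 5.2.6 lists among the bases of the safety analysis "clinically significant changes in the subject's physical examination, vital signs and clinical laboratory results". SAP 4.2.5 says that safety will be judged on abnormalities by body system in three classes: normal, abnormal not clinically significant (NCS) and abnormal clinically significant (CS). SAP 5.2.6.5 then plans one table, 14.3.11, for the variables "collected during physical examinations at baseline, the frequencies of normal, abnormal NCS and abnormal CS values will be reported by treatment group". For everything after baseline it says: "All individual measurements collected at baseline and during the subsequent visits will be provided in Listing 16.2.9.1".

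The baseline section, SAP 5.2.1, already has an entry reading "Physical exam at baseline by treatment group (Statistical table 14.1.3").

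Protocol 7.7 adds a second route. A clinically significant examination abnormality is recorded "as an AE occurring if after the start of study drug administration at Week 0, where the finding represents a change from Baseline".

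**Frequent TEAEs.** SAP 5.2.6.1 announces a table of the most frequent TEAEs but gives no cut-off. The cut-off appears only in the title of Table 14.3.4.2 in SAP 9.1: "Frequent Treatment Emergent Adverse Events (TEAEs) (>5% Overall) by System Organ Class (SOC) and Preferred Term (PT"). On the columns of the adverse event tables, SAP 5.2.6.1 says: "The following tables will be produced for the whole SAF population as well as by treatment group". Table 14.3.4.1 covers all TEAEs by system organ class and preferred term, with no threshold.

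**The concern.** A pre-dose table cannot show a treatment effect. If SAP 5.2.6.5 is followed as written, the examinations done on treatment are never summarised by arm. Secondary objective SO4 (tolerability and safety through Week 28) then lacks one of the comparisons that the SAP sets out, although the data are collected: Protocol Appendix A schedules an examination at Weeks 4 to 24 and at Week 28. A reader of the report would have to go through a patient-level listing to see whether normal findings became abnormal more often on PRM-151.

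The frequent-TEAE cut-off is a smaller matter of presentation. A threshold on both arms pooled can leave out an event that exceeds 5% of one arm.

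**Working it through.** **A. Physical examination against the other two domains named in SAP 5.2.6** (table numbers from SAP 9.1)

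| Domain | Baseline table | Post-baseline frequencies | Shift table |
|---|---|---|---|
| Laboratory | 14.1.4 to 14.1.9 | 14.3.8.2, 14.3.9.2, 14.3.10.2 | 14.3.8.3, 14.3.9.3, 14.3.10.3 |
| Vital signs | 14.1.2 | 14.3.12.3 | 14.3.12.4 |
| Physical examination | 14.1.3 and, as described, 14.3.11 | none | none |

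Overlap of 14.1.3 and 14.3.11: the first is on the All Treated Set (SAP 3.2). The second falls under SAP 5.2.6, which covers all subjects who received any study medication (the safety set of SAP 3.4). Both sets are randomised subjects with at least one dose. They differ only in grouping, as randomised against as treated. The two baseline tables therefore differ only if someone received the other treatment.

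What reaches a by-arm table after baseline:
- Change to abnormal CS: yes, as a TEAE by system organ class and preferred term, through Protocol 7.7.
- Change to abnormal NCS: no, listing only.
- Any shift by body system, with a denominator of patients examined: no.

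**B. Frequent-TEAE cut-off**

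The documents give no operating figure for this table. The denominators come from SAP 2.3.2: 117 planned, 78 on PRM-151 and 39 on placebo. That sample size reproduces. The expected difference is 0.75 − (0.75 × −1.5 + 0.25 × −3) = 2.625. With SD 5, two-sided alpha 0.10 and 2:1 allocation, this gives 34 placebo patients and 102 in total (power 80.4%), and 102 × 1.15 = 117.3.

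- Pooled rule: 5% of 117 = 5.85, so at least 6 patients are needed.
- PRM-151-only event: listed from 6/78 = 7.7%, omitted at 5/78 = 6.4%.
- Placebo-only event: listed from 6/39 = 15.4%, omitted at 5/39 = 12.8%.
- Either-arm rule: 5% of 78 = 3.9, so 4 patients (5.1%); 5% of 39 = 1.95, so 2 patients (5.1%).

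On the PRM-151 side, the either-arm rule adds only these counts (PRM-151 v placebo): 4 v 0, 4 v 1 and 5 v 0. Their two-sided Fisher p-values are 0.30, 0.66 and 0.17. On the placebo side it adds more, up to 0 v 5 (p = 0.003).

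Exact binomial chance that an event is listed:

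| True rate, PRM-151 / placebo | Pooled rule | Either-arm rule |
|---|---|---|
| 5% / 0% | 19.5% | 55.1% |
| 7.5% / 0% | 53.5% | 84.5% |
| 10% / 0% | 80.4% | 95.9% |
| 0% / 10% | 19.0% | 91.2% |

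Effect of the allocation ratio: a PRM-151-only event reaches 5% pooled at 0.05 × 117/78 = 7.5% of its arm. Under 1:1 it would need 0.05 × 2 = 10%. A placebo-only event needs 0.05 × 117/39 = 15%.

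**The case against.** **The adverse event route already covers what matters.** SAP 5.2.6 speaks of clinically significant changes, and that is the class that Protocol 7.7 turns into adverse events. Protocol 7.7 also has any worsening of a baseline condition recorded as an adverse event. This stands, and it is why the gap is minor. It does not close the gap. Protocol 7.8 sets the same adverse event rule for vital signs, and the SAP still plans shift tables for them. SAP 4.2.5 counts abnormal NCS as a class of the safety assessment, and that class does not become an adverse event by this rule. TEAE tables are organised by coded term, not by body system examined.

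**It may be a slip of wording.** SAP 9.1 titles 14.1.3 as a baseline table but gives 14.3.11, under safety results, no such limit. That is plausible. The remedy is then a correction of SAP 5.2.6.5, but a programmer who follows that section would still produce a baseline table.

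**The protocol does not ask for it.** Protocol 8.5.2 wants safety data summarised by time and arm, and names laboratory and vital signs data but not physical examination. True; the undertaking is the SAP's own.

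**Later examinations are abbreviated.** Only screening is complete (Protocol 7.7), and the systems covered afterwards are not specified, so some cells may be sparse. This is a reason to show denominators, not to omit the table.

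**A stronger reading is tempting:** that the examination table and the pooled 5% cut-off together keep a PRM-151 signal from showing, and that 2:1 allocation makes this worse. The documents do not support it. Table 14.3.4.1 gives every TEAE by arm with no threshold. Further tables cover related and serious TEAEs and intensity, and respiratory decline events and infusion related reactions have their own tables without a cut-off. The 2:1 ratio lowers the bar for a PRM-151-only event (7.5% instead of 10%). What the pooled rule mainly leaves out is events in excess on placebo.

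**Conclusion.** The point holds as a minor gap in SAP 5.2.6.5. Read literally, Table 14.3.11 largely repeats Table 14.1.3, and no table compares the arms on post-baseline examination findings by body system. Clinically significant changes remain visible as TEAEs, provided that sites apply Protocol 7.7. Shifts to abnormal NCS appear only in a listing. The primary analysis is not affected.

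The frequent-TEAE cut-off is a question of presentation only. It omits PRM-151 events in a narrow band (4 or 5 of 78 patients, with five or fewer in total) and placebo-only events below 6 of 39. Each of these is still in Table 14.3.4.1. The counts assume that the treated numbers equal the planned 78 and 39, and that the word overall in the title means both arms pooled; other treated numbers would move them slightly.

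**What to change.** 1. Reword SAP 5.2.6.5 so that Table 14.3.11 is a shift table by arm on the safety set: baseline class (normal, abnormal NCS, abnormal CS) against worst post-baseline class and against Week 28, per body system, limited to examinations before the first open-label dose. Show the number examined for each system, because later examinations are abbreviated. Leave the baseline display to Table 14.1.3. Cost: one table shell, no new data, and possibly sparse cells.

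2. Optional: state the frequent-TEAE rule in the text of SAP 5.2.6.1 as at least 5% in either arm, and align the title of Table 14.3.4.2. Cost: a somewhat longer table, since two placebo patients (5.1%) would be enough to list an event.

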5.2.6.6 Vital signs

- Quantitative descriptive statistics: mean, median, standard deviation, min, max based on raw values and change from baseline (Statistical tables 14.3.12.1 and 14.3.12.2)
- Qualitative descriptive statistics (individual patient changes):
 - Proportion of patients with abnormal values (Statistical table 14.3.12.3)
 - Shift Tables presenting the number of patients with normal/abnormal values at baseline and then at each cycle (Statistical table 14.3.12.4)

All individual measurements will be provided in Listing 16.2.9.2.

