7.8. Vital Signs

Vital signs, including measurement of systolic and diastolic blood pressure, pulse, heart rate, and O₂ saturation, are to be measured in the sitting position as per the schedule of events (Appendix A). At dosing visits, vital signs will be measured pre-dose as well as 1 hour post-dose and entered into the eCRF. Vitals signs should be monitored every 15 minutes during the infusion and captured on the source document.

If a vital sign abnormality is considered by the Investigator to be clinically significant, then the abnormality is to be recorded as part of the subject's medical history if occurring prior to start of dosing and as an AE occurring if after the start of study drug administration at Week 0, where the finding represents a change from Baseline.

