In the event of acute hypersensitivity or other infusion reaction, institutional protocol should be initiated, ECG should be performed, and a blood sample drawn for cytokines. Signs and symptoms of an infusion reaction may include the following: headache, fever, facial flushing, pruritis, myalgia, nausea, chest tightness, dyspnea, vomiting, erythema, abdominal discomfort, diaphoresis, shivers, hypertension, hypotension, lightheadedness, palpitations, urticaria and somnolence. Although unlikely, serious allergic reactions (e.g., anaphylaxis) may occur at any time during the infusion.

In the case of Grade 2 occurrence of signs and symptoms consistent with infusion related reaction, follow institutional protocol and reduce the rate of infusion of PRM-151 to half the initial rate; consider discontinue infusion of PRM-151 if symptoms do not respond to medical intervention. If signs and symptoms resolve with intervention including discontinuation of PRM-151, PRM-151 infusion may be restarted at half the initial rate.

In the case of Grade 3 or greater occurrence of signs and symptoms consistent with infusion related reaction, discontinue infusion of PRM-151.

In the event of an infusion related reactions, an ECG should be performed and a blood sample for cytokines should be collected as soon as possible after stabilization of the subject.

If PRM-151 resulted in signs and symptoms consistent with Grade 2 or 3 Infusion related reaction, infuse PRM-151 over 120 minutes and use the following premedication for all subsequent PRM-151 administration:

- Diphenhydramine 50 mg IV or clemastine 2 mg IV (or an equivalent dose of an antihistaminic drug)
- Dexamethasone 10 mg IV (or an equivalent dose of a long acting corticosteroid)

Infusion related reactions must be reported to Promedior as described in section 7.12.4.1, Reporting of Adverse Events of Special Interest.

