AEs will be coded by using the most current version of Medical Dictionary for Regulatory Activities (MedDRA) and summarized by system organ class, preferred term, and treatment group for the number and percent of AEs reported, the number of subjects reporting each AE, and the number of subjects with any AE. A by-subject AE data listing including onset and resolution dates, verbatim term, preferred term, treatment, severity, relationship to treatment, action taken, and outcome will be provided.

Safety data, including laboratory evaluations and vital signs assessments, will be summarized by time of collection and by treatment group. In addition, change from Baseline to any post-dose values will be summarized for vital signs and clinical laboratory results.

The frequency of subjects with abnormal safety laboratory results will be tabulated by treatment.

8.5.3. **Other Analyses**

8.5.3.1. **Subject Disposition**

A listing and table of proportions of subjects discontinuing the study for each reason will be provided by treatment / dose group. Details will be included in the Statistical Analysis Plan.

8.5.3.2. **Demographic and Baseline Characteristics**

Summary statistics will be provided for the demographic and baseline characteristics; details will be in the Statistical Analysis Plan.

8.5.3.3. **Subject Adherence**

Compliance with study drug will be computed for each subject as proportion of prescribed study drug actually taken. Details will be included in the Statistical Analysis Plan.

8.5.3.4. **Concomitant Medications**

A listing and table of proportions of subjects taking each concomitant medication will be provided. Details will be included in the Statistical Analysis Plan.

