4.2.4 Laboratory endpoints

During the study the following laboratory variables are recorded:

- **Hematology:** Hemoglobin, Hematocrit, Red Blood Cell, White Blood Cell, Neutrophils, Eosinophils, Basophils, Lymphocytes, Monocytes, Platelets.
- **Chemistry:** Sodium, Potassium, Chloride, Glucose, Calcium, AST, ALT, Total Bilirubin, Blood Urea Nitrogen, Bicarbonate, Albumin, Creatinine, Alkaline Phosphatase, Total Protein.
- **Coagulation:** Prothrombin Time, Partial Thromboplastin Time, International Normalized Ratio.

Each laboratory result will be categorized in 3 classes of abnormalities according to (see section 8):

- Normal
- Abnormal NCS
- Abnormal CS

Biological safety will be assessed based on raw test results and change from baseline in raw and categorized laboratory results.

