4.2.6 Vital signs

Vital signs, including Weight, Height, BMI, Heart rate, Respiratory rate, Oxygen saturation, Systolic blood pressure, Diastolic blood pressure are measured in the sitting position at each visit. Vital signs will be assessed based on both raw values and change from baseline to each visit in vital signs measurements. Safety will also be assessed based on abnormalities (normal, abnormal) in vital signs.

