Vital Sign abnormalities	
 • Heart rate: <50 or >90 • Respiratory rate: <12 or >20 • Body temperature: $<36.5^\circ\text{C}$ or $>37.5^\circ\text{C}$ • Diastolic Blood Pressure: <60 or >90 • Systolic Blood Pressure: <90 or >140 • Oxygen Saturation: <90
Event Duration	$(\text{End Date}) - (\text{Start Date}) + 1$
Total Lung Volume in ml (TLV)	Total lung volume (excluding vessel volume) in ml
Normal Lung Volume in ml (NLV)	NLV=Areas of Normal lung in ml + Mild Low Attenuation Area (LAA) in ml
% of Normal Lung Volume	$100 * (\text{NLV in ml}) / (\text{TLV in ml})$
% of mild Low Attenuation Areas (LAA)	$100 * (\text{mild LAA in ml}) / (\text{TLV in ml})$
% of moderate Low Attenuation Areas (LAA)	$100 * (\text{moderate LAA in ml}) / (\text{TLV in ml})$
% of severe Low Attenuation Areas (LAA)	$100 * (\text{severe LAA in ml}) / (\text{TLV in ml})$
% Ground Glass (GG)	$100 * (\text{GG in ml}) / (\text{TLV in ml})$

% Honeycombing (HC)	$100 * (\text{HC in ml}) / (\text{TLV in ml})$
% Reticular Changes (RC)	$100 * (\text{RC in ml}) / (\text{TLV in ml})$
Interstitial Lung Abnormalities (ILA) in ml	$(\text{ILA in ml}) = (\text{GG in ml}) + (\text{RC in ml}) + (\text{HC I ml})$
% Interstitial Lung Abnormalities (ILA)	$\% \text{ILA} = \% \text{GG} + \% \text{RC} + \% \text{HC}$
Historic FVC (% predicted)	$(\text{Historic FVC \% predicted}) = [\text{Historic FVC (mL)} / \text{Reference Result of FVC (mL) at baseline}] * 100$

9 Tables, Figures and Listings

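### The vital-sign tables put low and high values in one abnormal class, and the SAP neither says which value stands for a cycle nor plans a pre- to post-infusion summary

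*SAP*

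**What the plan says.** **Classes.** SAP section 4.2.6 states: "Safety will also be assessed based on abnormalities (normal, abnormal) in vital signs". The cut-offs are in SAP section 8, Derived data, under vital-sign abnormalities. Heart rate, respiratory rate, body temperature, diastolic pressure and systolic pressure each have a lower and an upper limit joined into one rule, such as "Systolic Blood Pressure: <90 or >140". Oxygen saturation has a lower limit only.

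**Tables.** SAP section 5.2.6.6 builds two tables on these classes: 14.3.12.3 (proportion abnormal) and 14.3.12.4, described as "Shift Tables presenting the number of patients with normal/abnormal values at baseline and then at each cycle". It also plans descriptive statistics, including minimum and maximum, for raw values and change from baseline (14.3.12.1 and 14.3.12.2), and a listing of all individual values.

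**Timing.** Protocol 7.8 says: "At dosing visits, vital signs will be measured pre-dose as well as 1 hour post-dose and entered into the eCRF". Readings taken every 15 minutes during the infusion go to the source document only. Protocol 8.5.2 plans summaries organised by when the data were collected, and adds that "change from Baseline to any post-dose values will be summarized for vital signs and clinical laboratory results". The vital-sign sections of the SAP speak only of visits and cycles and never mention a pre-dose or post-dose value.

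**Laboratory.** SAP section 4.2.4 says: "Each laboratory result will be categorized in 3 classes of abnormalities". The classes are normal, abnormal not clinically significant (NCS) and abnormal clinically significant (CS).

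**The concern.** A shift table should show who moved out of range and in which direction. With one abnormal class, a patient who starts high and becomes low stays in the same cell. A patient who starts normal and leaves the range is counted, but the reader cannot tell whether the value rose or fell.

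Direction matters for this product. Infusion reactions are a named risk in Protocol 1.5, and the listed signs in Protocol 7.12.1.2 include both directions of blood pressure: "hypertension, hypotension, lightheadedness, palpitations, urticaria and somnolence". Protocol 1.2 also reports one treated subject in the earlier IPF study with moderate hypotension and dizziness, judged possibly related, who stopped treatment. That event came just before a dose, so it is not evidence of a post-infusion effect, but it is a reason to tabulate low pressure separately from high.

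The second issue is which measurement is summarised. Acute effects would be sought in the 1-hour post-dose value, and the SAP does not say where that value goes.

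**Working it through.** The point concerns table structure. No error rate, power or sample size enters, and there is no figure in the plan to reproduce.

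**1. Apply the SAP section 8 limits to example values.**

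| Vital sign | Abnormal if | Example | SAP classes | Low/Normal/High |
|---|---|---|---|---|
| Systolic pressure | below 90 or above 140 | 150 to 85 | abnormal to abnormal | high to low |
| Diastolic pressure | below 60 or above 90 | 95 to 55 | abnormal to abnormal | high to low |
| Heart rate | below 50 or above 90 | 95 to 45 | abnormal to abnormal | high to low |
| Respiratory rate | below 12 or above 20 | 22 to 10 | abnormal to abnormal | high to low |
| Systolic pressure | as above | 120 to 85 | normal to abnormal | normal to low |
| Oxygen saturation | below 90 only | 92 to 88 | normal to abnormal | normal to low |

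Temperature (below 36.5 or above 37.5) behaves like the first four rows. Five of six rules merge the two directions.

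**2. How far must a value move to be hidden?** It must cross the whole normal range, that is, upper limit minus lower limit:
- systolic 140 − 90 = 50 mmHg
- diastolic 90 − 60 = 30 mmHg
- heart rate 90 − 50 = 40 per minute
- respiratory rate 20 − 12 = 8 per minute
- temperature 37.5 − 36.5 = 1.0 °C

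A completely hidden systolic shift therefore needs a fall of more than 50 mmHg. Loss of direction among patients who start normal needs no such move.

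**3. The proportion abnormal (14.3.12.3).** Take two patients: A goes from 150 to 120 and B from 120 to 85. One of two is abnormal before and one of two after. Both pressures fell, and the proportion did not change.

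**4. Which value represents a cycle?** SAP section 5.2.2 places the seventh cycle at Week 24, so the cycles start at Weeks 0, 4, 8, 12, 16, 20 and 24. Cycle 1 has infusions on Days 1, 3 and 5. Planned infusions: 3 + 6 = 9. Scheduled eCRF values per vital sign on dosing days: 9 × 2 = 18. Cycle 1 alone has 3 × 2 = 6, one of them the baseline; each later cycle has 2. No rule selects among them. The worst-value rules in SAP sections 5.4.2.1 and 5.4.3 cover retests and unscheduled visits only. SAP section 6, which records departures from the protocol, mentions no change to the safety summaries.

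**5. Why the choice matters.** Protocol 6.8 gives a half-life of 21 to 44 hours. Four weeks is 4 × 7 × 24 = 672 hours, which is 672 / 44 = 15.3 to 672 / 21 = 32 half-lives. A pre-dose value at Weeks 8 to 24 thus reflects almost no drug from the preceding infusion. SAP section 5.4.1 fixes baseline before the first study dose, so a post-dose change from baseline at Week 24 mixes 24 weeks of drift with the infusion effect. Only the difference from the same visit's pre-dose value separates them.

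**6. Laboratory.** SAP section 5.2.6.4 counts the three classes but does not restate the categories for the shift tables. No low/high split appears, and section 8, to which section 4.2.4 refers, contains no laboratory rule.

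**The case against.** Much of the signal can surface elsewhere:
- Suspected infusion reactions must be reported whatever their severity (Protocol 7.12.4.1). They are tabulated by arm, by intensity and seriousness, and by antibody status (SAP section 5.2.6.3).
- A vital-sign change that the investigator judges clinically significant after dosing is recorded as an adverse event (Protocol 7.8).
- If the post-dose readings are among the data summarised, a systolic value of 85 would limit the reported minimum, and a fall of 65 mmHg (150 − 85) would limit the minimum change.
- Every individual value is listed.

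For laboratory data, individual-value plots with the normal limits, eDISH plots and raw-value tables all show direction.

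This stands, and it keeps the point small. It does not close the gap. Adverse-event and reaction tables depend on investigator judgement, minima do not show who shifted, and a listing gives no comparison between arms.

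The post-dose phrase in Protocol 8.5.2 also covers laboratory results, so it could mean any value after the first dose rather than the 1-hour reading. That is fair. The same section still asks for summaries by collection time, and the 1-hour value is one of those times.

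A reader might infer three stronger things that the documents do not support:
- That only one vital-sign value per cycle will be analysed. The SAP says neither this nor the opposite; the rule is missing.
- That acute infusion effects cannot be seen at all. The outputs above show part of them.
- That laboratory results also fall into a single abnormal class. They have two, so a change in clinical significance would show.

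**Conclusion.** The point holds as a minor, inexpensive improvement to the safety tables. Two defects are established from the text. First, tables 14.3.12.3 and 14.3.12.4 lose direction for five of six vital signs, and a high-to-low change registers as no shift. Second, the SAP does not state which value enters each cycle and specifies no group-level pre- to post-infusion summary, although both values are collected in the eCRF. The laboratory shift tables lack direction too, but less is lost there because of the plots and the NCS/CS split.

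The number of patients affected cannot be derived. A reader might count everyone with raised pressure at baseline as hidden. The documents give no such rate, and it would be the wrong count: only patients who cross the whole normal range are hidden, and one who falls from high into the normal range does show a shift. Systolic and diastolic pressure also have separate rules, so a patient abnormal on one can still show a shift on the other.

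In practice the weight falls on blood pressure and heart rate. Temperature has a rule in SAP section 8 but is not named among the measured vital signs in SAP section 4.2.6 or Protocol 7.8. No efficacy conclusion or test depends on these tables.

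**What to change.** 1. In SAP section 8 and tables 14.3.12.3 and 14.3.12.4, replace normal/abnormal with Low/Normal/High, keeping the existing cut-offs. The shift table grows from 2 × 2 = 4 to 3 × 3 = 9 cells. Oxygen saturation needs only Low/Normal.
2. In SAP section 5.2.6.6, state which value (pre-dose, 1-hour post-dose, or worst) enters each cycle in tables 14.3.12.1 to 14.3.12.4, and how Days 1, 3 and 5 are handled in cycle 1.
3. Add a table, by arm and infusion number, of the change and the Low/Normal/High shift from that visit's pre-dose value to its 1-hour post-dose value.
4. In the laboratory shift tables (14.3.8.3, 14.3.9.3 and 14.3.10.3), state the categories and add low/high direction, keeping NCS/CS as a flag.

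The cost is SAP wording, table shells and a few more pages. The vital-sign values are already planned for the eCRF, so no new collection is needed. One limit remains: the 15-minute readings stay in the source document, so a transient low during an infusion that recovers before the 1-hour reading could still be missed by the new table.
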